### 5.3.3 Treatment and Procedures

The HepQuant Study encompasses the administration of the HepQuant SHUNT test, use of the HepQuant SHUNT Liver Diagnostic Kit, and monitoring of the test and test outcome. The procedures, components, and outputs of the HepQuant SHUNT test have been previously summarized in Section 3.1 of this document.

All other aspects of the subject’s care, treatments, management, and additional procedures are governed by the Gilead main clinical trial protocols. HepQuant will upload its test results to Gilead via secured portals and subsequently make requests of Gilead for specific analyses as defined via a collaborative research agreement between HepQuant and Gilead.

### **5.3.4 Administration of the HepQuant SHUNT test**

Detailed instructions are provided in the Instructions for Use (Appendix B). The HepQuant SHUNT test is performed after an overnight fast or after at least 5 hours of fasting during the daytime. The morning dose of drug(s) is held until after completion of the HepQuant SHUNT test. The HepQuant SHUNT test requires venous access via a standard indwelling intravenous catheter, preferably placed in an antecubital vein. An oral solution of 4D-CA and an injectable solution of 13C-CA mixed with 25% human serum albumin are administered simultaneously over approximately 1 minute. If a problem is encountered with administering compounds simultaneously, the test is to be re-scheduled. If a rescheduled visit falls outside of the Gilead protocol-defined windows, sites should contact their study monitor for further instruction.

Blood samples are obtained at baseline and at  $5\pm 1$ ,  $20\pm 2$ ,  $45\pm 5$ ,  $60\pm 5$ , and  $90\pm 5$  minutes after cholate administration. The serum is separated and sent to the HepQuant laboratory for quantification of concentrations of endogenous cholate, 4D-CA and 13C-CA. Clearances are calculated from AUCs and dose and DSI and SHUNT are derived from the clearances.

### **5.3.5 Procedures by Study Visit (Also refer to Schedule of Events)**

#### **Week -8 to Day -1 (Screening)**

- Informed Consent
- Review Inclusion/exclusion criteria
- Review continued eligibility
- Demographics
- Medical History
  - Hepatorenal Syndrome (Type I or Type II, treatment [if applicable])
  - Infection Related to Spontaneous Bacterial Peritonitis or SHUNT test or IV catheter (type, organism, treatment)
  - Hepatic Encephalopathy (treatment [if applicable], treatment type, whether controlled with treatment)
  - Ascites (treatment [if applicable], treatment type, whether controlled with treatment)
  - Variceal Hemorrhage (treatment [if applicable], treatment type)
- Physical Exam

### **Baseline/Day 1**

- Informed Consent (if not performed Week -8 to Day -1/Screening)
- Review inclusion / exclusion criteria (if not performed Week -8 to Day -1/Screening)
- Review continued eligibility
- Demographics (if not performed Week -8 to Day -1/Screening)
- Medical history (if not performed Week -8 to Day -1/Screening)
  - Hepatorenal Syndrome (Type I or Type II, treatment [if applicable])
  - Infection Related to Spontaneous Bacterial Peritonitis or SHUNT test or IV catheter (type, organism, treatment)
  - Hepatic Encephalopathy (treatment [if applicable], treatment type, whether controlled with treatment)
  - Ascites (treatment [if applicable], treatment type, whether controlled with treatment)
  - Variceal Hemorrhage (treatment [if applicable], treatment type)
  - Varices and Endoscopy (whether performed, date, presence of varices, size of largest varix)
    - Any EGD results that were collected as part of the subject's standard of care. Window is  $\pm$  18 months of the SHUNT test date. These reports will be de-identified of any HIPAA information and sent to HepQuant with the samples.
- Physical exam (if not performed Week -8 to Day -1/Screening)
- Vital signs (respiratory rate, temperature, blood pressure, heart rate, weight, and height)
- Prothrombin time, INR (see table below)
- Hematology (see table below)
- Chemistry (see table below)
- **HepQuant SHUNT Test**
- Patient survey
- Adverse events

### **Week 24**

- Review continued eligibility
- Medical History

- Hepatorenal Syndrome (Type I or Type II, treatment [if applicable])
- Infection Related to Spontaneous Bacterial Peritonitis or SHUNT test or IV catheter (type, organism, treatment)
- Hepatic Encephalopathy (treatment [if applicable], treatment type, whether controlled with treatment)
- Ascites (treatment [if applicable], treatment type, whether controlled with treatment)
- Variceal Hemorrhage (treatment [if applicable], treatment type)
- Varices and Endoscopy (whether performed, date, presence of varices, size of largest varix)
  - Any EGD results that were collected as part of the subject's standard of care. Window is  $\pm$  18 months of the SHUNT test date. These reports will be de-identified of any HIPAA information and sent to HepQuant with the samples.
- Vital signs (respiratory rate, temperature, blood pressure, heart rate, weight, and height) and laboratory tests
  - Prothrombin time, INR (see table below)
  - Hematology (see table below)
  - Chemistry (see table below)
- **HepQuant SHUNT Test**
- Patient survey
- Adverse events

### **Week 48**

- Review continued eligibility
- Medical history
  - Hepatorenal Syndrome (Type I or Type II, treatment [if applicable])
  - Infection Related to Spontaneous Bacterial Peritonitis or SHUNT test or IV catheter (type, organism, treatment)
  - Hepatic Encephalopathy (treatment [if applicable], treatment type, whether controlled with treatment)
  - Ascites (treatment [if applicable], treatment type, whether controlled with treatment)
  - Variceal Hemorrhage (treatment [if applicable], treatment type)
  - Varices and Endoscopy (whether performed, date, presence of varices, size of largest varix)

- Any EGD results that were collected as part of the subject's standard of care. Window is  $\pm$  18 months of the SHUNT test date. These reports will be de-identified of any HIPAA information and sent to HepQuant with the samples.
- Physical exam
- Vital signs (respiratory rate, temperature, blood pressure, heart rate, weight, and height)
- Prothrombin time, INR (see table below)
- Hematology (see table below)
- Chemistry (see table below)
- **HepQuant SHUNT Test**
- Patient survey
- Adverse events

#### **Week 240 (Not applicable to GS-454-4378)**

- Review continued eligibility
- Demographics
- Medical history
- Hepatorenal Syndrome (Type I or Type II, treatment [if applicable])
- Infection Related to Spontaneous Bacterial Peritonitis or SHUNT test or IV catheter (type, organism, treatment)
- Hepatic Encephalopathy (treatment [if applicable], treatment type, whether controlled with treatment)
- Ascites (treatment [if applicable], treatment type, whether controlled with treatment)
- Variceal Hemorrhage (treatment [if applicable], treatment type)
- Varices and Endoscopy (whether performed, date, presence of varices, size of largest varix)
  - Any EGD results that were collected as part of the subject's standard of care. Window is  $\pm$  18 months of the SHUNT test date, for the final study visit. These reports will be de-identified of any HIPAA information and sent to HepQuant with the samples.
- Physical exam
- Vital signs (respiratory rate, temperature, blood pressure, heart rate, weight, and height)

- Prothrombin time, INR (see table below)
- Hematology (see table below)
- Chemistry (see table below)
- **HepQuant SHUNT Test**
- Patient survey
- Adverse events

Local Laboratory Tests*		
Hematology	Chemistry	Coagulation Profile
WBC	Sodium	Prothrombin time
RBC	Potassium	INR
Hemoglobin	Calcium	
Platelets	Urea Nitrogen	
Neutrophils	Creatinine	
Lymphocytes	Albumin	
Monocytes	Bilirubin	
Eosinophils	Alanine Aminotransferase	
Basophils	Aspartate Aminotransferase	
Neutrophils (%)	Alkaline Phosphatase	
Lymphocytes (%)	Glucose	
	Chloride	

\*To be collected prior to cholate/SHUNT test administration at each study visit

## 6.0 Descriptions, Risks, Justifications

### 6.1. Drug Safety Definitions

**Abuse:** Persistent or sporadic intentional excessive use of a medicinal product by a patient or clinical trial subject.

**Adverse Event (“AE”):** Any untoward medical occurrence in a patient or clinical investigation subject administered a medicinal product and which does not necessarily have to have a causal relationship with this treatment. An Adverse Event (AE) can therefore be any unfavourable and/or unintended sign (including an abnormal laboratory finding, for example), symptom, or disease temporally associated with the use of a

medicinal product, whether or not considered related to the medicinal product. AEs may also include pre- or post-treatment complications that occur as a result of protocol mandated procedures, lack of efficacy, overdose or drug Abuse/Misuse reports. Pre-existing events that increase in severity or change in nature during or as a consequence of participation in the clinical study shall also be considered AEs.

**Adverse Reaction (“AR”):** An untoward medical occurrence (unintended or noxious responses) considered causally related to an investigational or authorized medicinal product at any dose administered. Adverse Reactions may arise from Medication Errors, uses outside what is foreseen in the protocol or prescribing information (off-label use), Misuse and Abuse of the product, Overdose or Occupational Exposure where applicable.

**Development Safety Update Report (“DSUR”):** A report providing an annual review and evaluation of pertinent safety information collected during the reporting period to summarise the current understanding and management of identified and potential risks, describe new safety issues that could impact clinical trial subjects and provide an update on the status of the development program.

**Medication Error:** Any unintentional error in the prescribing, dispensing or administration of a medicinal product while the medication is in the control of a healthcare professional, patient or consumer.

**Misuse:** Use of a medicinal product that is intentional and inappropriate and not in accordance with its authorized product information.

**Occupational Exposure:** Exposure to a medicinal product as a result of one’s professional or non-professional occupation.

**Off-label Use:** Where a medicinal product is intentionally prescribed by a Health Care Professional for a medical purpose not in accordance with the authorized product information with respect to indication, route, dose or patient population (e.g. the elderly). For avoidance of doubt, Off-Label Use will not apply in clinical trials.

**Overdose:** Administration of a quantity of a medicinal product given per administration or cumulatively which is above the maximum recommended dose as per the protocol or in the product labelling. The Parties agree that in the course of conducting a clinical study,

the terms of the clinical study protocol (as fully approved by all applicable bodies) overrides the local product labelling.

**Pregnancy Reports:** Reports of pregnancy following maternal or paternal exposure to the product.

**Product Complaints:** Complaints arising from potential deviations in the manufacture, packaging or distribution of the medicinal product.

**Serious Adverse Event (“SAE”) / Serious Adverse Reaction (“SAR”):** An event or any untoward medical occurrence that at any dose either:

- a) Results in death; or
- b) Is life-threatening

The term “life-threatening” in the definition of “serious” refers to an event in which the patient was at risk of death at the time of the event; it does not refer to an event which hypothetically might have caused death if it were more severe; or:

- c) Requires in-patient hospitalisation or prolongation of existing hospitalisation; or
- d) Results in persistent or significant disability/incapacity; or
- e) Results in a congenital anomaly/birth defect; or
- f) Results in a medically important event or reaction.

**Explaining a medically important event:** AEs requiring medical and scientific judgment to determine if expedited reporting is appropriate. Such events may not be immediately life-threatening or result in death or hospitalisation but may jeopardise the patient or may require intervention to prevent one of the other outcomes constituting SAEs. Medical and scientific judgement should be exercised in deciding whether an event is a medically important event. Examples of medically important events include intensive treatment in an emergency room or at home for allergic bronchospasm; blood dyscrasias or convulsions that do not result in hospitalisation; or development of drug dependency or drug Abuse. For the avoidance of doubt, infections resulting from contaminated medicinal product shall be considered a medically important event and subject to expedited reporting requirements.

**Special Situation Reports (“SSR”):** One of a) Pregnancy, b) Abuse, c) Medication Error, d) Misuse, e) Off-Label Use, f) Overdose, g) Lack of Effect, h) AEs in infants following exposure from breastfeeding, i) AEs associated with Product Complaints or arising from Occupational Exposure. For the avoidance of doubt this applies to all reports including reports in a pediatric or elderly population.

**Unexpected:** An AE or AR where the nature and/or severity of the reaction is not consistent with the term or description used in the investigator brochure or product labeling.

**NOTE:** This is not an exhaustive list and any safety information will be reported to Gilead DSPH and appropriate regulatory bodies.

## 6.2 Test Administration Risks

### **BLOOD DRAWS**

Drawing blood from a vein may cause local pain, bruising, occasional lightheadedness, fainting, and very rarely, infection at the site of the blood draw.

### **FASTING**

Fasting could cause dizziness, headache, stomach discomfort, or fainting.

### **INTRAVENOUS CATHETER**

In some cases, having an intravenous catheter inserted into your vein can cause infection or inflammation where it goes under the skin. In rare cases, it can cause a blood clot in the vein.

## 6.3 Cholates

### **6.3.1 Stable Isotope Labels (13C and 4D)**

The labels used in the HepQuant test are cold and stable – they are NOT RADIOACTIVE and do not expose the individual to any radioactivity. No special monitoring is required. The HepQuant tests measure the clearance of 2 cholates labeled with molecular probes (carbon-13 (13C), and 4 deuteriums (4D)). Cholates are naturally occurring endogenous compounds found in the human body and 13C and D are also naturally occurring non-

radioactive cold stable isotopes. Cholates labeled with stable isotopes in the amounts administered in the HepQuant tests have no known harmful effects. Because clearance of cholate from the blood is a liver specific flow-dependent function, measuring cholate clearance is a minimally-invasive method for assessing the severity of liver disease in intact humans.

Cholates are naturally-occurring in the human body. The cholates in the HepQuant SHUNT test are modified by the addition of stable, cold (NON-RADIOACTIVE) isotopes. Neither naturally occurring nor the modified cholates used in the HepQuant SHUNT test have any known deleterious or adverse effects when given intravenously or orally in the doses used in HQ tests. The serum cholate concentrations that are achieved by either the intravenous or oral doses are similar to the serum concentrations of bile acids that occur after the ingestion of a fatty meal.

### **6.3.2 Manufacturing of Labeled Cholates**

The cholate testing compounds will be purchased. The test compound 2,2,4,4-d4-cholate (d4-CA) has been previously studied under FDA Investigational New Drug (IND) application 65,123. The test compound 24-13C-cholate (13C-CA) has been previously studied under FDA IND 65,121. No adverse events occurred in over 1400 test administrations. These INDs are legacies to the current IDEs that govern use of the HepQuant SHUNT test in the Gilead trials. To date, the cholates used in this study have not been associated with any adverse events. However, they are still considered experimental and there may be unknown risks.

### **6.3.3 Formulations**

Cholates are purchased in powder form and both powders are dissolved in sodium bicarbonate solution (USP grade) to achieve concentrations of 4 mg/mL and passed through 0.22 micron filters. The absolute concentrations of 4D-cholate in the 4D-cholate solution and the 13C-cholate in the 13C-cholate solution will be defined by LCMS methods – concentrations typically range from 3.5 to 4.2 mg/mL.

d4-CA aliquots of 10 mL (~40 mg) will be transferred to sterile glass vials and stored at ambient temperature. For 13C-CA aliquots of 5.5 mL (~22 mg) will be transferred to sterile glass vials and stored at ambient temperature. Sterility and absence of pyrogens will be confirmed prior to use.

A central pharmacy will formulate the test compounds, perform the sterile filtering, and prepare the sterile aliquots. Once concentration and sterility are confirmed the cholate solutions are transferred to a kit maker for assemblage of the HepQuant SHUNT Liver Diagnostic Kit.

NOTE: The vial containing the oral dose of 4D-CA contains the exact amount of 10 mL of 4D-CA (~40 mg). But, in contrast, the vial containing the intravenous dose of 13C-CA contains approximately 5.5 mL of 13C-CA (~22 mg) – an excess of 0.5 mL (2 mg) to allow for aspiration of exactly 5 mL into a syringe. Accurate testing requires administration of the entire 10 mL of 4D-CA (~40 mg) oral solution; and, exactly 5 mL of 13C-CA (~20 mg) intravenously.

#### **6.3.4 Tolerability and Safety**

Over 1400 HepQuant SHUNT tests have been performed in over 650 subjects without any untoward effects. In the GILEAD SOLAR-1 study of ledipasvir/sofosbuvir/ribavirin treatment of hepatitis C in decompensated cirrhosis or in liver transplant recipients, HepQuant SHUNT tests were performed 5 times over 48 weeks in each of 31 study participants. All 31 subjects completed a survey of their experience with the HepQuant SHUNT test after a mean ( $\pm$ SD) of  $4.5\pm 0.6$  tests. The patient reported outcome survey is given in Appendix C. Pain was rated  $0.5\pm 0.8$ , where 0 was no pain and 10 was severe pain. Discomfort was rated  $0.3\pm 0.5$ , where 0 was no discomfort and 10 was severe discomfort. Inconvenience was rated  $0.4\pm 0.9$ , where 0 was no interference with daily activity and 10 was complete inability to conduct usual daily activity.

The recording of time commitment indicated <3 hours in 23 cases and >3 h in 8 cases. The overall experience with the test was rated  $9.5\pm 1.1$ , where 0 was very negative and 10 was very positive. Willingness to undergo additional testing was rated  $9.1\pm 1.8$ , where 0 was definitely not willing and 10 was very willing.

Ten subjects (32%) experienced 14 SAEs during the treatment course. The SAEs were 2 bouts of spontaneous bacterial peritonitis in the same patient, two admissions for anasarca in the same patient, and one each of dysphagia, myocardial infarction, biliary stricture, incarcerated umbilical hernia, nausea, hepatic encephalopathy, chest pain, diarrhea, anemia, and fever. None of the SAEs were attributed to HepQuant tests and only one, encephalopathy, was attributed to study drug (ribavirin).

### **6.3.5 Unknown / Unexpected Risks**

The two cholates used in the HepQuant test for this study are labeled with stable (non-radioactive) forms of carbon and hydrogen that are found in nature and can be measured in blood. These forms of cholate have been registered with the FDA since 2002, and their use in humans has been monitored since that time. To date, the cholates used in this study have not been associated with any complaints or side effects. However, they are still considered experimental and there may be unknown risks.

The subject will be told of any new information that might cause him/her to change his/her mind about continuing to take part in this study.

### **6.3.6 Reporting**

HepQuant is not collecting any information regarding adverse events, serious adverse events, and Special Situation Reports (SSR) with respect to the GILEAD products used in the GILEAD clinical trials. HepQuant is only monitoring the SHUNT test and procedure for AEs, SAEs, and Special Situations that are solely related to the HepQuant SHUNT test. HepQuant will inform study sites and GILEAD of AEs, SAEs, and SSRs that are documented to occur and are related to the HepQuant SHUNT test.

HepQuant will be responsible for the management of safety data from the Study and any associated regulatory reporting obligations for individual or periodic safety reports to the appropriate authorities and clinical investigators and applicable IRB/EC, in compliance with all applicable laws and the requirements of the IRB/EC.

The contact information for reporting of safety issues or adverse reactions is:

[name]  
Manager, Clinical Accounts & Quality

U.S.A.

The contact information for reporting of safety issues, product concerns or feedback is:

Ring Central  
[contact]  
[[contact]](mailto:[contact])

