### **6.5 Intravenous Catheter**

Placing the indwelling intravenous catheter will cause minor pain and discomfort. With any blood draw there is a small risk of hematoma and a very small risk of a blood clot (1 in 100) or infection (1 in 1000). Over 1500 HepQuant SHUNT tests or the prototypical dual cholate research tests have been performed on over 600 individuals and most had the test multiple times. There has never been an adverse event - the risk from the test is

very small. A questionnaire will be completed by the subject at each of the testing periods to log their experience and tolerability of HQ tests (Appendix C).

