### **6.6.4 HepQuant Study Versus Gilead Clinical Trial**

The HepQuant Study encompasses only the administration of the HepQuant SHUNT test, use of the HepQuant SHUNT Liver Diagnostic Kit, and monitoring of the test and test outcome. We do not anticipate any additional risks or issues related to the HepQuant SHUNT test other than those described above. AEs, SAEs, and SUSARs related to the HepQuant SHUNT test will be evaluated by HepQuant and reported by HepQuant to the appropriate regulatory authorities, including local IRBs and FDA and Gilead drug safety.

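### Section 6.3.6 monitors only events solely related to the SHUNT test, while other sections say related or set no causal limit, so events of mixed or uncertain cause may be left out of the device's safety record

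*Combined protocol and SAP*

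**What the plan says.** Section 6.3.6 (Reporting) first says that HepQuant gathers no adverse-event information on the Gilead products. It then restricts HepQuant's own monitoring of the test and procedure to events "that are solely related to the HepQuant SHUNT test". The next sentence commits HepQuant to inform sites and Gilead of events "that are documented to occur and are related to the HepQuant SHUNT test", this time without *solely*.

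Other sections are wider:

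- Section 6.6.4: "AEs, SAEs, and SUSARs related to the HepQuant SHUNT test will be evaluated by HepQuant".
- Section 6.1 defines an adverse event as one that "does not necessarily have to have a causal relationship with this treatment", and again "whether or not considered related to the medicinal product". A closing note to that section has any safety information passed to Gilead drug safety and to regulators.
- Section 5.3.5 lists adverse events as an item at Baseline and Weeks 24, 48 and 240, with no causal condition.
- Section 6.6.1 has site staff enter the study's data into an electronic data capture system.

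**The concern.** The SHUNT test is an investigational drug/device combination (section 1.1.1), and its record of no test-related events is offered as support for its safety (sections 3.1.1, 6.3.2 and 6.5). The value of such a record depends on which events are considered before attribution. In section 6.3.6 the causal condition is attached to monitoring, so an event would have to be judged wholly due to the test before it came into view.

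Every subject is also in a drug trial and has advanced NASH. An event that could be due to the test or to one of these would rarely qualify as solely due to the test. If sites follow the sentence literally, such events may be missing from the device's record. If some sites follow it and others follow the visit lists, recording may differ across up to 15 sites.

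**Working it through.** The question is one of wording. The plan states no figure to reproduce.

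**Step 1. The scopes side by side.**

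| Place | What it governs | Causal condition |
|---|---|---|
| 5.3.5, testing visits | Items at the visit | None |
| 5.3.5, infection item under medical history | Prompt for details | Linked to bacterial peritonitis, the test or the catheter; not sole cause |
| 6.1, AE definition | What counts as an AE | None |
| 6.1, closing note | Reporting to Gilead and regulators | None |
| 6.3.6, monitoring sentence | What HepQuant monitors | Solely related |
| 6.3.6, next sentence | What HepQuant tells sites and Gilead | Related and documented |
| 6.6.4 | Evaluation and reporting to authorities | Related |

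There are three scopes: all events, related events and solely related events. No sentence ranks them.

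**Step 2. The two sentences of 6.3.6.** An event that is related to the test but has a second possible cause falls inside the duty to inform and outside the monitoring scope. Taken literally, the section obliges HepQuant to report events that it does not undertake to monitor. The text gives no relatedness scale and no rule for an uncertain cause.

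**Step 3. Do mixed causes arise in this design?**

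- Section 6.2 lists headache as a possible effect of fasting for the test.
- Section 3.2.1 lists headache among the commonest events on selonsertib.
- Section 5.3.4 holds the morning study dose until the test is finished, so the dose can follow the test closely.
- Section 1.3 describes the parent trials as double-blind, so while treatment is blinded a site cannot rule out study drug even for a subject on placebo.

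A headache later that day could have either cause, and a site could seldom call it solely test-related. The same reasoning applies where the underlying liver disease is a plausible cause.

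**Step 4. Which causes are not examples.** Albumin is in the kit (3.1.4, 6.4.1). The catheter and fasting are listed as test administration risks (6.2). Doses are held because of the test (5.3.4, 7.2.1). The monitoring sentence in 6.3.6 covers the test and its procedure, so reactions to these belong to the test and should pass even the strict condition.

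**Step 5. How many tests the rule covers.** Enrolment is capped at 100 (5.1). Section 8.2.3 gives 5 + 4 = 9 STELLAR subjects, each with four planned tests. At most 100 − 9 = 91 others come from GS-US-454-4378, each with three.

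- Tests at most: 91 × 3 + 9 × 4 = 273 + 36 = 309.
- Tests after baseline at most: 309 − 100 = 209.

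These are upper limits on occasions. The documents give no rate of mixed-cause events, so the number that might be omitted cannot be computed.

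**Step 6. The protocol's own precedent.** For the earlier parallel study in hepatitis C, section 6.3.4 lists the serious events first and then states attribution. Its counts agree: 2 + 2 + 10 single events = 14, and 10/31 = 32.3%, given as 32%. None was attributed to the test. That order, listing before attribution, is the one the monitoring sentence of 6.3.6 reverses.

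**The case against.** The best defence is that *solely* only divides work between two sponsors. The sentence before it disclaims events on the Gilead products, and the visit lists, the infection prompt, the patient survey at each testing visit and the data capture system all give events a way into the record. The note in 6.1 is broader still. Much of this stands. It shows that omission is possible rather than certain, so the documents do not support a reading that mixed-cause events will be lost. It does not settle the point, because a division of responsibility needs a rule for shared events, and *solely* assigns those to neither sponsor's test record.

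A reader might also infer more in four ways:

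- **That 6.3.6 contradicts the AE definition.** A broad definition with a narrower reporting scope is not in itself a contradiction. The firm inconsistency is *solely related* against *related* and against the unrestricted visit item.
- **That a clean record would follow almost automatically.** Hematoma, catheter infection, fainting at a blood draw and albumin hypersensitivity could all meet the strict condition.
- **That the catheter clot risk in 6.5, set against the earlier zero-event record, shows past under-recording.** Those tests are not shown to have been run under this sentence, and the mismatch may lie in the quoted risk. It is a separate question about 6.5.
- **That nothing returns parent-trial events to HepQuant for attribution.** The body text describes no such route, but Appendices D and F are listed in the contents and were not in the text reviewed, so its absence cannot be asserted.

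**Conclusion.** The point holds as an unresolved inconsistency of scope. The narrowest wording sits in the section that says what HepQuant monitors. Followed literally, it may leave out events with a mixed or uncertain cause, chiefly where the test procedure overlaps with study drug or underlying disease.

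The size is unknown. The wording applies to at most 309 tests, and overlap with study drug is most plausible at the 209 after baseline. Those counts assume full enrolment to the cap and every planned test done.

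The conclusion rests on the body text alone. The missing appendices may add collection detail, but they would not remove the conflict between the sentences of 6.3.6 and sections 5.3.5 and 6.6.4. This is a modest point, worth correcting because the product is investigational and the change is nearly free.

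**What to change.** Delete *solely* in section 6.3.6 and state one scope there that matches the visit lists and section 6.6.4:

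- adverse events are recorded at the testing visits, as 5.3.5 already provides;
- the relatedness of each to the test or its procedure is rated;
- events rated at least possibly related stay in the device's safety record and are reported, including those for which study drug or underlying disease is also a possible cause.

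The sentence on Gilead products can remain, with a clause saying that it does not remove an event that may also be due to the test.

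The cost is protocol wording, a relatedness field if the data capture form lacks one, and slightly more recording at visits that already list adverse events. The event count may look less favourable than under the strict wording, and the report should say that possibly related events are included.
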